Pressure ulcer assessment ⁶ (digital photograph taking, investigator's photo evaluation) - Ulcer size (Using a scale) - Complete healing status	V ⁷	V	V	V	V	V	V	V	V	V	V	V	V	V	V	V	V	V	V	V	V	V	V	V	V	V

Item	Schedule	Screening		Treatment period																		Closing					
		1*	2*	3	4	5	6	7	8	9	10	11	12	13	14**												
		-14d~0d	1d (±1d)	5d* (±1d)	8d (±1d)	12d* (±1d)	15d (±1d)	19d* (±1d)	22d (±1d)	26d* (±1d)	29d (±1d)	33d* (±1d)	36d (±1d)	40d* (±1d)	43d (±1d)	47d* (±1d)	50d (±1d)	54d* (±1d)	57d (±1d)	61d* (±1d)	64d (±1d)	68d* (±1d)	71d (±1d)	75d* (±1d)	78d (±1d)	82d* (±2d)	85d (±2d)
PUSH		V			V				V				V				V			V							V
Self-dressing training		V		V	V	V	V	V	V	V	V	V	V	V	V	V	V	V	V	V	V	V	V	V	V	V	V
Dressing change frequency review				V	V	V	V	V	V	V	V	V	V	V	V	V	V	V	V	V	V	V	V	V	V	V	V
Infection sign checklist ⁸ (CSSC)		V		V	V	V	V	V	V	V	V	V	V	V	V	V	V	V	V	V	V	V	V	V	V	V	V
Subject diary distribution ⁹		V		V	V	V	V	V	V	V	V	V	V	V	V	V	V	V	V	V	V	V	V	V	V	V	V
Subject diary return				V	V	V	V	V	V	V	V	V	V	V	V	V	V	V	V	V	V	V	V	V	V	V	V
Concomitant medication/treatment review	V	V		V	V	V	V	V	V	V	V	V	V	V	V	V	V	V	V	V	V	V	V	V	V	V	V
Adverse event review		V		V	V	V	V	V	V	V	V	V	V	V	V	V	V	V	V	V	V	V	V	V	V	V	V

* Visit 1 and Visit 2 can take place on the same day.

** Subjects who have complete healing during the study or are withdrawn from the study will have all tests scheduled for V14.

¥ Subject do not make a site visit but perform self-dressing.

† Except for Randomization visit, Home Health Care system through study coordinator will be used for those subjects who aren't able to make a visit during the treatment period. Physical examination and measuring weight may be exempt in case of replacing visit with Home Health Care.

- Blood pressure, pulse, body temperature measurement
- Laboratory tests: If test findings within 2 weeks prior to the consent date are available, they may be used instead of screening findings.
 - Hematology: WBC, RBC, platelet, WBC count, Hb, Hct
 - Blood chemistry: AST, ALT, ALP, creatinine, BUN, total bilirubin, glucose, protein, albumin, gamma GTP, TSH (TSH is conducted at screening only)
- Urine hCG pregnancy test is conducted only in women of child-bearing potential.
- The investigational device is changed twice weekly; additional changes are allowed depending on the pressure ulcer condition, without any limitation to frequency.

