8.2 Exclusion criteria

- 1) Any study ulcer of the NPUAP Stage I, II or IV
- 2) Diabetic ulcer or Venous ulcer (or stasis ulcer)
- 3) Past history of surgical treatment within 1 year or irradiation at the target pressure ulcer within 1 year
- 4) Hypersensitivity reaction to this product or povidone-iodine
- 5) Hyperthyroidism or thyroid disorder requiring drug treatment
- 6) Signs of a current underlying systemic infection (sepsis/bacterial infection/tuberculosis) or cellulitis or osteomyelitis
- 7) Type 1 diabetes
- 8) Current malnutrition
- 9) Heavy smoker: Current smoking level of ≥ 1 pack (20 cigarettes)/day of tobacco
- 10) Drug or alcohol addiction
- 11) Requirement of immunosuppressants during the study or current chemotherapy or radiotherapy
- 12) Application of other investigational product/medical device within 1 month prior to the

investigational device application (1d)

13) Pregnant or breastfeeding women

14) Other renal, hepatic, neurological, immunological disorder that may interfere with the wound healing process, at the discretion of the investigator

9. Target number of subjects and the rationale

The target number of subject enrollment is 20 subjects, with 10 subjects per group.

This study has a purely explorative goal so that no formal sample size calculation will be conducted but it was planned to enroll 10 subjects per group as the minimum sample size to achieve study objectives from a scientific perspective.

- ✓ Medifoam group: 10 subjects
- ✓ Betafoam group: 10 subjects

Even if a subject is withdrawn from the study, the subject will not be replaced.

10. Study method

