12.1.4 Visit 14 (End-of-Study visit/85d or early completion)

The following tests will be conducted at the End-of-Study visit or early completion (only in subjects with complete healing).

- ① Conduct the physical examination.
- ② As vital signs, measure blood pressure, pulse, and body temperature.
- ③ Measure body weight.
- ④ Conduct laboratory tests (hematology, blood chemistry).
- ⑤ After removing the investigational device, take a photograph of the study ulcer, conduct the investigator's photo evaluation, and record the pressure ulcer size by a Scale and complete healing status.
- ⑥ Check the infection signs using the CSSC (Clinical Signs and Symptoms Checklist).
- ⑦ Conduct standard dressing.
- ⑧ After conducting the pressure ulcer assessment, record the PUSH score.
- ⑨ Review concomitant medication and adverse events (all adverse events, local adverse events at the study ulcer).
- ⑩ At the last visit, investigational devices that have been prescribed but not used are to be returned.
- ⑪ Based on the subject diary, record the frequency of self-dressing beyond once-weekly in the Case Report Form.

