## 3. Study Design

---

[figure not shown]
This is a single-center, randomized, 2-arms, open-label pilot study.

Subjects who consent to the study will be assessed for eligibility with screening tests. Subjects can have a 2-week screening period.

After screening, subjects who meet the inclusion/exclusion criteria will apply Medifoam® or Betafoam® for 12 weeks, after randomization. Targeted subjects are outpatient clinic or hospitalized patients. Subjects will make once weekly site visits.

During the treatment period, dressing is performed twice weekly, but additional dressing changes are allowed, depending on the condition of the pressure ulcer, such as excessive exudates at the study ulcer. Nevertheless, the frequency of additional dressing is limited to twice daily. On the weekly site visit days, the investigator(or clinical research coordinator) will change the dressing; on other occasions, the subject or guardian will perform self-dressing. Subjects who achieve complete healing of the target pressure ulcer within 12 weeks will have early completion.

Efficacy assessment is conducted for a total of 12 times at a 1-week interval, after the investigational device application (8d, 15d, 22d, 29d, 36d, 43d, 50d, 57d, 64d, 71d, 78d, 85d). At each efficacy assessment, the investigator (or clinical research coordinator) should take a digital photograph of the target pressure ulcer and retain it as a source document.

---

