### **Early completion criteria**

Subjects who achieve complete healing\* of the target pressure ulcer will complete the study early. Subjects who can complete the study early will undergo all tests scheduled for the End-of-Study (85d) visit and then complete the study.

(\* Complete healing: Defined as the condition with the epithelial tissue covering 100% of the study ulcer, no abrasion or ulceration, intact dermis and epidermis.)

---

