## 9. Handling Missing Values

---

---

For subjects with a missing value during the study or who are withdrawn from the study prior to study completion, efficacy analysis will be conducted by applying the LOCF (Last observation Carried Forward), only in case such subjects have available endpoints of main interest assessment results after the investigational device application. However, in case of missing values for other endpoints and safety endpoints, raw data will be used for analysis, without applying LOCF.

---

---

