### 13. TLFs

#### 1) Disposition of Subjects

Table 0101 Disposition of Subjects who participated in the study

	Medifoam	Betafoam	Total
Subjects who signed the Informed Consent form	xx(xx.xx%)	xx(xx.xx%)	xx(xx.xx%)
Screening	xx(xx.xx%)	xx(xx.xx%)	xx(xx.xx%)
Screening Failure	xx(xx.xx%)	xx(xx.xx%)	xx(xx.xx%)
Reason for Screening Failure1	xx(xx.xx%)	xx(xx.xx%)	xx(xx.xx%)
Reason for Screening Failure2	xx(xx.xx%)	xx(xx.xx%)	xx(xx.xx%)
Reason for Screening Failure3	xx(xx.xx%)	xx(xx.xx%)	xx(xx.xx%)
Randomized	xx(xx.xx%)	xx(xx.xx%)	xx(xx.xx%)
Reason for Discontinuation 1	xx(xx.xx%)	xx(xx.xx%)	xx(xx.xx%)
Reason for Discontinuation 2	xx(xx.xx%)	xx(xx.xx%)	xx(xx.xx%)
Reason for Discontinuation 3	xx(xx.xx%)	xx(xx.xx%)	xx(xx.xx%)
Subjects who completed the trial (including Early completion)	xx(xx.xx%)	xx(xx.xx%)	xx(xx.xx%)

Table 0102 Detailed reports on discontinued subjects

Treatment Group	Screening No.	Randomization No.	Informed Consent Date	Discontinuation Date	Reason for Discontinuation

Table 0103 Analysis Set

	Medifoam	Betafoam	Total
Randomized	xx(xx.xx%)	xx(xx.xx%)	xx(xx.xx%)
Reason1 for Safety excluded	xx(xx.xx%)	xx(xx.xx%)	xx(xx.xx%)
Reason2 for Safety excluded			
Safety Set	xx(xx.xx%)	xx(xx.xx%)	xx(xx.xx%)
Reason1 for FAS excluded	xx(xx.xx%)	xx(xx.xx%)	xx(xx.xx%)
Reason2 for FAS excluded	xx(xx.xx%)	xx(xx.xx%)	xx(xx.xx%)
FAS	xx(xx.xx%)	xx(xx.xx%)	xx(xx.xx%)

2) Demographics  
Analysis Set: FAS

Table 0201 Demographics

		Medifoam	Betafoam	Total	p-value
Gender	Male	xx(xx.xx%)	xx(xx.xx%)	xx(xx.xx%)	0.xxxx‡
	Female	xx(xx.xx%)	xx(xx.xx%)	xx(xx.xx%)	
	Total	xx(xx.xx%)	xx(xx.xx%)	xx(xx.xx%)	
Age (Years)	N	xx	xx	xx	0.xxxx*
	Mean±Std	xx.xx±x.xx	xx.xx±x.xx	xx.xx±x.xx	
	Median	xx.xx	xx.xx	xx.xx	
	Min~Max	xx.xx~xx.xx	xx.xx~xx.xx	xx.xx~xx.xx	
Age (Categorical)	19~29	xx(xx.xx%)	xx(xx.xx%)	xx(xx.xx%)	0.xxxx‡
	30~39	xx(xx.xx%)	xx(xx.xx%)	xx(xx.xx%)	
	40~49	xx(xx.xx%)	xx(xx.xx%)	xx(xx.xx%)	
	50~59	xx(xx.xx%)	xx(xx.xx%)	xx(xx.xx%)	
	60~69	xx(xx.xx%)	xx(xx.xx%)	xx(xx.xx%)	
	70<	xx(xx.xx%)	xx(xx.xx%)	xx(xx.xx%)	
	Total	xx(xx.xx%)	xx(xx.xx%)	xx(xx.xx%)	
Body Weight (kg)	N	xx	xx	xx	0.xxxx*
	Mean±Std	xx.xx±x.xx	xx.xx±x.xx	xx.xx±x.xx	
	Median	xx.xx	xx.xx	xx.xx	
	Min~Max	xx.xx~xx.xx	xx.xx~xx.xx	xx.xx~xx.xx	
Height (cm)	N	xx	xx	xx	0.xxxx*
	Mean±Std	xx.xx±x.xx	xx.xx±x.xx	xx.xx±x.xx	
	Median	xx.xx	xx.xx	xx.xx	
	Min~Max	xx.xx~xx.xx	xx.xx~xx.xx	xx.xx~xx.xx	
Breast Feeding (Female Only)	Yes	xx(xx.xx%)	xx(xx.xx%)	xx(xx.xx%)	0.xxxx‡
	No	xx(xx.xx%)	xx(xx.xx%)	xx(xx.xx%)	

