Figure 0601 Time to complete healing of ulcer within 12 weeks

[figure not shown]

Table 0603 Pressure ulcer size by each time point and change from 1d (baseline)

Time points		Medifoam	Betafoam	Total	P-value
Visit2(1d)	N	xx	xx	xx	0.xxxx*
	Mean±Std	xx.xx±x.xx	xx.xx±x.xx	xx.xx±x.xx	
	Median	xx.xx	xx.xx	xx.xx	
	Min~Max	xx.xx~xx.xx	xx.xx~xx.xx	xx.xx~xx.xx	
Visit3(8d±1d)	N	xx	xx	xx	0.xxxx*
	Mean±Std	xx.xx±x.xx	xx.xx±x.xx	xx.xx±x.xx	
	Median	xx.xx	xx.xx	xx.xx	
	Min~Max	xx.xx~xx.xx	xx.xx~xx.xx	xx.xx~xx.xx	
Visit4~Visit14	..(Middle Part omitted)..				

Note) \*: t-test, ¥ : Wilcoxon rank sum test

Table 0604 Pressure ulcer size reduction rate based on scale at each time point

Time points		Medifoam	Betafoam	Total	P-value
		n(%)	n(%)	n(%)	
Visit3(8d±1d)	N	xx	xx	xx	0.xxxx*
	Mean±Std	xx.xx±x.xx	xx.xx±x.xx	xx.xx±x.xx	
	Median	xx.xx	xx.xx	xx.xx	
	Min~Max	xx.xx~xx.xx	xx.xx~xx.xx	xx.xx~xx.xx	
	P-value(within)	0.xxxx#			

Visit4~Visit13	..(Middle Part omitted)..				
Visit14(85d±2d)	N	xx	xx	xx	0.xxxx*
	Mean±Std	xx.xx±x.xx	xx.xx±x.xx	xx.xx±x.xx	
	Median	xx.xx	xx.xx	xx.xx	
	Min~Max	xx.xx~xx.xx	xx.xx~xx.xx	xx.xx~xx.xx	
	P-value(within)	0.xxxx#			

Note) \*: t-test, ¥ : Wilcoxon rank sum test #: Paired t-test, \$: Wilcoxon signed rank test

Table 0605 Sub-analysis on Pressure ulcer size reduction rate based on scale at each time point by Use of topical antibiotics

Use of Topical antibiotics	Time points	Medifoam	Betafoam	Total	P-value	
Topical antibiotics used	Visit3(8d±1d)	N	xx	xx	xx	0.xxxx*
		Mean±Std	xx.xx±x.xx	xx.xx±x.xx	xx.xx±x.xx	
		Median	xx.xx	xx.xx	xx.xx	
		Min~Max	xx.xx~xx.xx	xx.xx~xx.xx	xx.xx~xx.xx	
	Visit4~Visit13	..(Middle Part Omitted)..				
	Visit14(85d±2d)	N	xx	xx	xx	0.xxxx*
		Mean±Std	xx.xx±x.xx	xx.xx±x.xx	xx.xx±x.xx	
		Median	xx.xx	xx.xx	xx.xx	
Min~Max		xx.xx~xx.xx	xx.xx~xx.xx	xx.xx~xx.xx		
Topical antibiotics Not used	Visit3(8d±1d)	N	xx	xx	xx	0.xxxx*
		Mean±Std	xx.xx±x.xx	xx.xx±x.xx	xx.xx±x.xx	
		Median	xx.xx	xx.xx	xx.xx	
		Min~Max	xx.xx~xx.xx	xx.xx~xx.xx	xx.xx~xx.xx	
	Visit4~Visit13	..(Middle Part Omitted)..				
	Visit14(85d±2d)	N	xx	xx	xx	0.xxxx*
		Mean±Std	xx.xx±x.xx	xx.xx±x.xx	xx.xx±x.xx	
		Median	xx.xx	xx.xx	xx.xx	
Min~Max		xx.xx~xx.xx	xx.xx~xx.xx	xx.xx~xx.xx		

Note) \*: t-test, ¥ : Wilcoxon rank sum test

Table 0606 Sub-analysis on Pressure ulcer size reduction rate based on scale at each time point by Use of glucocorticoids

Use of glucocorticoids	Time points		Medifoam	Betafoam	Total	P-value
Glucocorticoids used	Visit3(8d±1d)	N	xx	xx	xx	0.xxxx*

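### The SAP does not say what a healed ulcer contributes to the visit rows after early completion, and it labels a Visit 14 that can fall early as 85d±2d

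*SAP*

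**What the plan says.** **Protocol.** Section 12.1.4 is headed "Visit 14 (End-of-Study visit/85d or early completion", and its text limits the early visit to subjects with complete healing. The footnote to the schedule of study activities is wider: "Subjects who have complete healing during the study or are withdrawn from the study will have all tests scheduled for V14".

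**SAP, assessments and endpoints.** Section 3: "Efficacy assessment is conducted for a total of 12 times at a 1-week interval", from 8d to 85d. Section 7.1 lists ulcer size and size reduction rate at each time point among the endpoints of main interest, and section 8 compares the arms on both by t-test.

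**SAP, status of healed subjects.** Section 5: "Subjects who achieve complete healing\* of the target pressure ulcer will complete the study early". Table 0101 has a row "Subjects who completed the trial (including Early completion", so they are not counted as discontinued.

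**SAP, missing values.** For endpoints of main interest, section 9 applies LOCF "For subjects with a missing value during the study or who are withdrawn from the study prior to study completion", provided a post-application assessment exists. Other endpoints and safety endpoints are analysed as raw data without LOCF. Protocol 15.1 says the same.

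**SAP, table shells.** Tables 0604-0606, 0701, 0901-0902 and 1001-1004 label the last row "Visit14(85d±2d" (the closing bracket follows). Table 0603 does not. It prints only a visit range ending at Visit 14.

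**The concern.** A subject who heals at 29d has the end-of-study tests then and leaves. Visits 7 to 13 do not take place for that subject. The SAP does not say whether the subject counts at those visits as 0 cm² and 100% reduction, or not at all. The subject has neither withdrawn nor, on a strict reading, missed a visit during the study, so the LOCF rule does not clearly apply.

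If healed subjects are left out, each interim mean and t-test for two endpoints of main interest covers only ulcers that have not yet healed. The best outcomes are removed, and more of them from the arm that heals more. The sub-analysis Tables 0605-0606 have the same gap.

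PUSH does not depend on how the LOCF rule is read. With LOCF excluded, a subject healed at 29d has no value in the 43d, 57d and 71d rows.

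The row label is a separate matter. Healing can be recorded at any visit from 8d, so a row headed 85d±2d could mix assessments made after about 1 to 12 weeks of treatment. If the printed window were enforced instead, early completers would lose their only scheduled post-baseline laboratory values, because laboratory tests are done only at screening and at completion.

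**Working it through.** The plan gives no figure to reproduce. Protocol 9 states that "no formal sample size calculation will be conducted", and neither document assumes a healing rate. The healing and shrinkage inputs below are therefore assumptions, used only to show the size of the effect.

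**Inputs from the documents**
- 10 subjects per arm (Protocol 9).
- Visit days 1 + 7k for k = 1 to 12, which gives 8d to 85d, 12 visits as stated.
- Reduction rate = (size on 1d − size at visit) / size on 1d × 100 (SAP 7.1). The sizes in the recording example of Protocol 12.2.4 (5, 3.5, 2.2, 0 cm²) give 30%, 56% and 100%, so a healed ulcer contributes 100%.

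**Assumptions**
- 4 subjects healed at 29d in one arm and 1 in the other.
- Unhealed ulcers in both arms shrink linearly to 50% at 85d. At 57d their reduction is 50 × (57 − 1)/(85 − 1) = 50 × 56/84 = 33.3%.

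**Formula.** With h healed of 10 and unhealed mean m, the visit mean is (100h + (10 − h)m)/10 if 0 cm² is carried, and m on 10 − h subjects if it is not.

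| Row and handling | 4 healed | 1 healed | Difference |
|---|---|---|---|
| 57d, 0 cm² carried | (400 + 6 × 33.3)/10 = 60.0% | (100 + 9 × 33.3)/10 = 40.0% | 20.0 |
| 57d, healed subjects absent | 33.3% (N = 6) | 33.3% (N = 9) | 0.0 |
| 85d, 0 cm² carried, or exit value filed as Visit 14 | (400 + 6 × 50)/10 = 70.0% | (100 + 9 × 50)/10 = 55.0% | 15.0 |
| 85d, window enforced and nothing carried | 50.0% (N = 6) | 50.0% (N = 9) | 0.0 |

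**Range.** With equal m in both arms, the difference with carrying is (difference in number healed) × (100 − m)/10, and 0 without carrying. For 5 versus 2 healed it is 24, 18 or 12 points at m = 20, 40 or 60. Within one arm with 4 healed, the visit mean is 52 versus 20%, 64 versus 40%, or 76 versus 60%.

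**PUSH.** Scores are scheduled at 1d, 15d, 29d, 43d, 57d, 71d and 85d. A closed ulcer with no area and no exudate scores 0 + 0 + 0 = 0 on the tool in Protocol 12.2.11, a reduction of 100%. The no-LOCF rule keeps that value out of each later scheduled row. It reappears at 85d only if the exit visit is filed as Visit 14.

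**The case against.** The strongest answer is that the SAP can be read to do the right thing. A missing value during the study may cover the unattended visits of an early completer, and LOCF would then carry 0 cm² through to 85d. Protocol 12.1.3 requires size and healing status at each interim visit, so the zero is recorded on its own day. The shells also print day windows, which points towards filing by date. This stands as a possible reading. No sentence selects it, and Table 0101 points the other way.

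A reader might go further than the documents allow in four ways:
- **That the last pre-healing size is carried past healing** (2.2 cm², 56%, in the recording example). This would need the healing visit's own record to be empty, although Protocol 12.1.3 requires it and the example enters 0 cm² at 29d.
- **That the Week 12 size result is wrong.** If the exit value is filed as Visit 14, a healed ulcer is 0 cm² there just as under LOCF, and a withdrawn subject's exit value is what LOCF would supply. The result changes only if the window is enforced and nothing is carried.
- **That SAP 9 forbids exit values in the PUSH, laboratory and vital-sign rows.** An observed exit value is raw data. The fault there is the 85d label.
- **That the arm that heals more always loses its advantage.** The fall to exactly 0 points follows from assuming equal shrinkage of unhealed ulcers. With unequal shrinkage, what remains is the difference among unhealed ulcers, of either sign.

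The trial is also a 20-subject exploratory pilot, which limits the consequences.

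**Conclusion.** The point holds as a gap in the analysis rules. Two plausible readings of SAP 9 give different interim-visit means and t-tests for ulcer size and size reduction rate. On the strict reading those rows describe unhealed ulcers only. On the other there is no size error. For PUSH, the stated rule itself removes healed subjects from the later rows.

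Under the assumptions above, the choice moves the 57d between-arm difference from 20 points to 0. Across the range shown, a difference of 12 to 24 points disappears. Number healed is unaffected, as is time to healing, which is counted in days from baseline. For laboratory and vital-sign tables the issue is labelling. The documents do not establish that healed values will be dropped, only that nothing settles the matter. It should be settled before analysis, because the trial is open-label and endpoints of main interest should not depend on an unstated programming choice.

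**What to change.** Add to SAP 9:

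> Early-completion and exit assessments are assigned to the scheduled visit nearest the actual day. For subjects with complete healing, ulcer size is set to 0 cm² (100% reduction) and PUSH to 0 at every later scheduled visit through 85d.

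State that the PUSH part is a derivation rule for healed ulcers and an exception to the no-LOCF rule, since Protocol 15.1 carries the same exclusion. State also that the rule assumes the ulcer stays closed, which is not observed after exit.

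Rename the Visit 14 rows in Tables 0901-0902 and 1001-1004 to *End of participation* and show the day of assessment. A further row limited to 85d±2d is optional. Do not limit the PUSH row to that window unless the healed-ulcer rule is in place, because the window alone would drop healed subjects.

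Reconcile Protocol 12.1.4 with the schedule footnote on whether withdrawn subjects have the Visit 14 tests.

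The cost is two sentences, a visit-mapping step and relabelled shells. No new data are needed. The optional 85d±2d rows would have a smaller N.
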